## List of Abbreviations and Definition of Terms

AE	Adverse Event
AE SI	Adverse Event of Special Interest
ALP	Alkaline phosphatase
ALT	Alanine transaminase
aPTT	activated Partial Thromboplastin Time
AST	Aspartate transaminase
ATC	Anatomical Therapeutic Chemical classification
ATM	Ataxia-telangiectasia Mutated
AUC	Area under the curve
BLRM	Bayesian 2-parameter Logistic Regression Model
BMI	Body Mass Index
BOR	Best Overall Response
BSA	Body Surface Area
BUN	Blood Urea Nitrogen
CDISC	Clinical Data Interchange Standards Consortium
CI	Confidence Interval
COVID-19	Coronavirus disease 2019
CMH	Cochran-Mantel-Haenszel
CALCIO	Corrected Calcium and Ionized Calcium
CR	Complete Response
(e)CRF	(electronic) Case Report Form
CSR	Clinical Study Report
CTCAE	Common Terminology Criteria for Adverse Events
CTMS	Clinical Trial Management System
CV	Coefficient of Variation
DL	Dose Level
DLT	Dose Limiting Toxicity
DNA	Deoxyribonucleic Acid
DoR	Duration of response
ECG	Electrocardiogram

ECOG	Eastern Co-operative Oncology Group
eDISH	Drug-Induced Serious Hepatotoxicity
FAS	Full Analysis Set
FU	Follow-up
GCP	Good Clinical Practice
$\gamma$ -H2AX	Gamma Histone Family Member X
HR	Hazard Ratio
HRQoL	Health-related quality of life
IAP	Integrated Analysis Plan
ICE	Intercurrent Event
ICH	International Conference on Harmonization
IDMC	Independent Data Monitoring Committee
ICD-O	International Classification of Diseases for Oncology
IPD	Important Protocol Deviation
IRC	Independent Review Committee
ITT	Intention To Treat
IVRS	Interactive Voice Response System
KM	Kaplan-Meier
LLN	Lower Limit of Normal
LLOQ	The lower limit of quantitation
MedDRA	Medical Dictionary for Regulatory Activities
MH	Mantel-Haenszel
MTD	Maximum Tolerated Dose
NA	Not Applicable
nd	Not done
NCI-CTCAE	National Cancer Institute – Common Terminology Criteria for Adverse Events
OR	Objective Response
ORR	Objective Response Rate
OS	Overall Survival
p-ATM	Phosphorylated Ataxia-Telangiectasia Mutated
Pd	Pharmacodynamics

---

PD	Progressive Disease or Protocol Deviation or Pharmacodynamics
PFS	Progression Free Survival
PT	Preferred Term
PGx	Pharmacogenetics/Pharmacogenomics
PK	Pharmacokinetics
PKAS	Pharmacokinetic Analysis Set
PR	Partial Response
QTcF	QT interval corrected using Fridericia's formula
RECIST	Response Evaluation Criteria in Solid Tumors
RDE	Recommended Dose for Expansion
SAE	Serious Adverse Event
SAF	Safety Analysis Set
SCR	Screening analysis set
SMC	Safety Monitoring Committee
SD	Stable Disease or Standard Deviation
SDTM	Study Data Tabulation Model
SMC	Safety Monitoring Committee
SOC	System Organ Class
TEAE	Treatment-Emergent Adverse Event
ULN	Upper Limit of Normal
WBC	White Blood Cell Count
WHO-DD	World Health Organization Drug Dictionary

### 3 Modification History

Unique Identifier for Version	Date of IAP Version	Author	Changes from the Previous Version
1.0	09 November 2021	PPD	Initial Version
2.0	19 December 2022	PPD	
Only final analysis will be performed. DLTs will be presented only by DLT analysis set. Non-relevant analyses removed:
 

• Table on baseline tumor assessment

• ECOG shift table

• Subsequence anti-cancer therapy

• Prior Anti-cancer Therapy by ATC and PT

### 4 Purpose of the Integrated Analysis Plan

The purpose of this Integrated Analysis Plan (IAP) is to document technical and detailed specifications for all the analyses of data collected for protocol MS201512\_0010 including Part 1A (dose escalation) and Part 1B (preliminary food effect cohort).

Results of the analyses described in this IAP will be included in the Clinical Study Report (CSR) or in separate reports. Additionally, the planned analyses identified in this IAP may be included in regulatory submissions or future manuscripts. Any post-hoc, or unplanned analyses performed to provide results for inclusion in the CSR but not identified in this prospective IAP will be clearly identified in the CSR.

The IAP is based on Section 9 (Statistical considerations) of the protocol amendment version 4.0 dated 27 October 2022 and is prepared in compliance with International Conference on Harmonization (ICH E9). It describes analyses planned in the protocol and protocol amendments. Details of the Safety Monitoring Committee (SMC) analyses for regular review of the participants' safety are provided in appendix.

### 5 Objectives and Estimands

Objectives and Estimands: M4076 Monotherapy Dose Escalation (Part 1A) and Preliminary Food Effect Assessment (Part 1B)

Objectives	Estimands Attributes	IAP section
Primary		
To determine dose-toxicity relationship and MTD (if reached) of M4076 monotherapy in participants with advanced solid tumors.	
Endpoints:
 
 
Occurrence of Dose Limiting Toxicities (DLTs).
 
Occurrence of adverse events (AEs) and treatment-related AEs.
 
Occurrence of clinically significant changes in vital signs, laboratory parameters, and 12-lead electrocardiogram (ECG) findings.
 
 
Strategy for handling intercurrent events:
 
For DLTs:
 
 
Discontinuation of treatment (> 20% planned treatment missed during DLT period) to prevent a DLT: composite strategy (to be considered a DLT).
 
Discontinuation treatment administrations not due to DLT or preventing a DLT (> 20% of planned treatment missed during DLT period): participant not considered in DLT analysis.
 
 
For other endpoints: All available data from participants in safety analysis set will be used.
 
Population: Patients with advanced solid tumors, who are intolerant or have no effective standard therapies available to them.
 
Population level summary:
 
 
DLT probability as estimated using BLRM and credibility interval (only applicable for DLTs).
 
Standard summary statistics.
 
	Section 15.1 Section 15.2, 15.3 Section 15.4, 15.5, 15.6
Secondary		
To determine the recommended dose for expansion (RDE) of M4076 monotherapy in participants with advanced solid tumors.	
Endpoints:
 
 
In addition to safety and tolerability, changes from baseline for the following Pd biomarkers may be considered for determining the RDE: ATM pathway readouts such as, but not limited to, p-ATM, γ-H2AX and p-CHK2 in blood and tumor.
 
In addition, pharmacokinetic (PK) data will be used to support determination of the RDE.
 
	Section 15 Section 16.1
To characterize the PK profile of M4076 monotherapy in participants with advanced solid tumors.	
Endpoints:
 
 
PK parameters of M4076 in plasma after single dose and multiple doses.
 
Urine PK parameters (e.g., renal clearance) will be characterized in Part 1B if data permits.
 
	Section 16.1

Objectives	Estimands Attributes	IAP section
To evaluate preliminary clinical activity parameters of M4076 monotherapy in participants with advanced solid tumors.	Endpoints: 

Objective response (OR) according to RECIST 1.1 assessed by Investigator.

Duration of response (DoR) according to RECIST 1.1 assessed by Investigator.

Progression Free Survival (PFS) according to RECIST 1.1 assessed by Investigator.

	Section 14
To assess the effect of food on the PK of M4076 administered as a single dose under fed/fasting conditions in a cohort of participants with advanced solid tumors at the RDE from Part 1A.	Endpoints: Fed/fasted ratio of M4076 plasma PK parameters: $AUC_{0-\text{last}}$ , $AUC_{0-\infty}$ and, $C_{\max}$ when administered as a single dose with or without food.	Section 16.1
To assess changes in pharmacodynamic markers of M4076 activity in tumor and blood during M4076 monotherapy.	Endpoints: Absolute and relative changes over time from baseline of ATM pathway readouts, such as, but not limited to p-ATM, p-CHK2 and $\gamma$ -H2AX.	Section 16.2

CCI

## 6 Overview of Planned Analyses

The following analyses are planned for this trial:

- Safety Monitoring Committee (SMC) analyses (See IAP for SMC in Appendix 18.3)
- Final analysis for dose escalation and food effect cohort (Part 1A and Part 1B)

Statistical analyses (except for SMCs) will be performed on the basis of CDISC SDTM data. These SDTM data contain as clean as possible eCRF data as well as external data for central laboratory biomarker data, tumor assessment results by Investigator and DLT decisions from SMC.

Statistical analyses for SMCs will be performed on the basis of eCRF/external data.

A data review meeting will be held prior to any database lock. In addition, no database can be locked until this IAP has been approved (except for emergency).

All planned analyses identified in the Clinical Study Protocol and in this IAP will be performed.

## **6.1 Analyses for SMC meetings**

Details of analyses for SMC meetings will be specified in a separate IAP, provided in Appendix 18.2.

## **6.2 Primary Analysis for dose escalation and food effect cohort (Part 1A and Part 1B)**

The cutoff for the primary analysis of the safety, available PK, available Pd and preliminary antitumor activity data from Part 1A and Part 1B will be triggered when all participants have reached either the first on-treatment tumor assessment, or experienced death or premature withdrawal for any reason, whichever comes first.

All trial data up to the primary analysis cutoff date will need to be in-house, all data queries resolved, and the database locked for primary analysis.

This analysis will be the main analysis. All planned analyses as specified in the TLF table of contents for primary analysis will be performed.

## **6.3 Final Analysis for dose escalation and food effect cohort (Part 1A and Part 1B)**

Final analyses to report further efficacy and safety data will be performed once the End of Study has been reached. Please refer to the study protocol for details on when participants are considered to have completed the study.

All planned analyses as specified in the TLF table of contents for final analysis will be performed.

## **7 Changes to the Planned Analyses in the Clinical Study Protocol**

There are no changes to the planned analyses in the clinical study protocol.

## **8 Analysis Sets and Subgroups**

### **8.1 Definition of Analysis Sets**

#### **Screening Analysis Set (SCR)**

The Screening analysis set includes all participants who signed the informed consent.

### Full Analysis Set (FAS) / Safety Analysis Set (SAF)

The analysis set will include all screened participants, who received at least one dose of any study intervention. Analyses will consider participants as treated.

Participants will be classified according to the dose actually received. See Section 9 for details on determination of actual dose level. The Full Analysis Set (FAS) and the Safety Analysis Set (SAF) are identical. In outputs this analysis set will be denoted by 'FAS/SAF'. Analyses of safety and efficacy will be based on this analysis set.

### Dose Limiting Toxicity Analysis Set (DLT)

The DLT Set will include all participants who received at least one dose of study intervention and meet at least one of the following criteria:

- Experienced at least one DLT during the DLT period, regardless of the administered number of doses of study intervention/completion in the DLT period
- Received at least 80% of the planned cumulative dose during the DLT period of each study intervention and completed the DLT period
- Additionally, participants who did not receive 80% of the planned total dose of study intervention, but at least 80% dosing of a different dose cohort and finished the DLT period are eligible for the DLT analysis set to be analyzed in the highest dose cohort for which they received 80% of dosing.

The final decision on evaluability for dose escalation analysis will be made by the SMC (e.g. considering relevant deviations from dosing schedule).

### PK Analysis Set (PKAS)

The Pharmacokinetic (PK) Analysis Set (PKAS) is a subset of the FAS/SAF and will consist of all participants, who receive at least one dose of study intervention, and provide at least one measurable post-dose concentration. A measurement below lower limit of quantification (BLQ) is considered a valid measurement. Participants will be analyzed per the actual study intervention they received. All PK analyses will be based on the PK Analysis Population.

### Pd Analysis Set

The pharmacodynamics (Pd) Analysis Set will consist of all participants, who receive at least one dose of study intervention, have no clinically important protocol deviations or important events affecting Pd, and provide the baseline and at least one measurable Pd endpoint postdose. Participants will be analyzed per the actual study intervention they received. All Pd analyses will be based on this analysis population.

### Analyses per Analysis Set

The following table summarizes the use of the analysis sets in the different analyses.

Analyses	DLT	FAS/SAF	PKAS	Pd
DLT: Primary	✓			
Safety and Tolerability		✓		
Baseline Characteristics		✓		
Previous and Concomitant Therapies		✓		
Compliance and Exposure		✓		
Efficacy		✓		
Pharmacokinetic			✓	
Pharmacodynamic				✓

DLT = Dose Limiting Toxicity; FAS = Full Analysis Set; SAF = Safety Analysis Set; PK = Pharmacokinetic Analysis Set; Pd = Pharmacodynamic

Note: Safety, PK and Pd will be described by actual dose which might differ from planned dose.

All other analyses will be described by planned dose, according to Intention-to-Treat principle. For more details, see Section 9.

## 9 General Specifications for Data Analyses

The results of this study will be reported using summary tables, figures, and data listings, as appropriate. All data will be summarized by study part (Part 1A and Part 1B), dose level (and regimen if different regimens tested), and by dietary status (“Fed” and “Fasted”) and/or scheduled time point, as applicable.

### Definition of actual dose

Unless otherwise specified, analyses of safety, efficacy and PK parameters will be conducted by actual dose. In this open label, unblinded study, actual dose is determined by considering study drug compliance during the DLT evaluation period (first 21 days from first dose of M4076) and whether the subject experienced a DLT (as per SMC determination). If a different regimen is tested, all subjects remain in the regimen to which they were assigned (i.e. subjects cannot be assigned to a different pre-specified dose level with a different dosing scheme).

In this context, compliance is defined as the cumulative actual dose taken by the subject divided by the cumulative cohort-level planned dose the subject was expected to receive. The planned dose level will be taken from the electronic case report form (eCRF) “Cohort”. The following table will be used to determine actual dose level:

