**Table 1 Actual Dose Assignment**

Compliance of planned dose	DLT Status	Compliance relative to other pre-specified dose levels	Actual dose
> 100%	Any	≥ 80% a higher pre-specified dose level	Higher pre-specified dose level
> 100%	Any	< 80% a higher pre-specified dose level (or no higher dose level)	Planned dose level
≤ 100%	DLT	Any	Planned dose level
≥ 80% and ≤ 100%	No DLT	Any	Planned dose level
< 80%	No DLT	≥ 80% of a lower pre-specified dose level	Lower pre-specified dose level
< 80%	No DLT	< 80% of the lowest pre-specified dose level (or no lower dose level)	Lowest received pre-specified dose level*

\*Patient is not evaluable for DLT analysis set

Note: In case a subject received >120% cumulative dose of the planned dose but ≤ 80% of the next higher pre-specified dose the data of this subject will not be considered in Pd and efficacy summary outputs. The data will be displayed in listings and line plots but with a footnote stating the actual cumulative dose.

In the event there are subjects whose 'actual' dose differs from the planned dose, disposition, compliance and exposure will be described by both planned and 'actual' dose.

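### SAP Table 1 sets the safety-table dose level from 21-day cumulative mg, so missed doses alone can place a participant under a daily dose never taken

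*SAP*

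**What the plan says.** SAP Section 9 (Definition of actual dose) makes actual dose the default grouping: "Unless otherwise specified, analyses of safety, efficacy and PK parameters will be conducted by actual dose". It then explains that "actual dose is determined by considering study drug compliance during the DLT evaluation period (first 21 days from first dose of M4076"), together with DLT status as decided by the SMC. Compliance is cumulative mg taken divided by the cumulative mg planned for the cohort.

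Table 1 applies this as follows.
- A participant with no DLT and under 80% of plan, whose total is "≥ 80% of a lower pre-specified dose level", is assigned to that lower level.
- If the total does not reach 80% of even the lowest level, or no lower level exists, the assignment is "Lowest received pre-specified dose level". Only this row carries the footnote "Patient is not evaluable for DLT analysis set".
- A participant above 100% of plan whose total reaches 80% of a "higher pre-specified dose level" is moved up.
- A participant with a DLT and no more than 100% of plan stays at the planned level.

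Where planned and actual dose differ, "disposition, compliance and exposure will be described by both planned and" actual dose. The note to the analysis-set table in SAP 8.1 says "Safety, PK and Pd will be described by actual dose which might differ from planned dose", and puts everything else under planned dose. SAP 15.2 presents adverse events by dose level.

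**The concern.** Protocol 6.6.2.1 bars dose modification during the Part 1A DLT period. A low 21-day total therefore normally means full doses missed, not a lower daily dose taken. The downward row treats the two situations alike. Only the last row of Table 1 refers to a level actually received.

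The primary objective is the dose-toxicity relationship, and protocol 9.2 plans cohorts of about 3. One relabelled participant takes events observed at a higher daily dose out of that column and adds them to a small lower-dose column. The both-ways display covers disposition, compliance and exposure; it is not extended to adverse-event summaries.

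Two related texts also disagree.
- **DLT set against estimand.** The third criterion for the DLT set (protocol Table 15, SAP 8.1) admits a participant who finished the DLT period below 80% of plan but with at least 80% of another cohort's dosing. The estimand (protocol Table 6, SAP Section 5) leaves out participants who missed more than 20% of treatment for reasons other than a DLT or its prevention.
- **Efficacy grouping.** The SAP 8.1 note implies planned dose. Section 9 says actual dose.

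**Working it through.** The documents give no worked figure for this rule, so there is none to reproduce. I applied Table 1 directly.

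**Inputs.** Window of 21 days and the mg-based compliance ratio (SAP Section 9); 80% thresholds (Table 1); once-daily dosing; potential levels of 100, 200, 300, 400 and 600 mg, with 50 mg as fallback (protocol 4.1.1). Protocol 9.2 and 9.4.2.1 list 100, 200, 400 and 600 mg. Appendix 12 lists 50, 100, 200, 400 and 600 mg.

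**Two reading assumptions.**
1. The denominator is the full 21-day plan.
2. Where several lower levels qualify, the highest is used. Table 1 says only that the total must reach 80% of some lower level; the highest-level tie-break is written only for the DLT set.

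**Rule.** For daily dose d and k doses taken, the planned level is kept if k/21 ≥ 0.80. Since 17/21 = 81.0% and 16/21 = 76.2%, this needs 17 doses. Otherwise the participant moves to the highest lower level L with d × k ≥ 0.80 × 21 × L.

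**Thresholds (0.80 × 21 × L).** 100 mg: 1,680 mg. 200 mg: 3,360 mg. 300 mg: 5,040 mg. 400 mg: 6,720 mg.

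**Example: 400 mg on Days 1–12, then dosing stops for a logistical reason.**
- Total: 12 × 400 = 4,800 mg.
- Against plan: 4,800 / 8,400 = 57.1%, below 80%.
- Against 300 mg: 4,800 / 6,300 = 76.2%, does not qualify.
- Against 200 mg: 4,800 / 4,200 = 114.3%, qualifies.
- Label: 200 mg, a daily dose never taken.

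The same label applies from 9 doses (3,600 mg, 85.7% of the 200 mg total) to 12 doses.

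| Daily dose taken | Number of doses and resulting label, any level list | Depends on whether 300 mg counts |
|---|---|---|
| 200 mg | 9–16: 100 mg | – |
| 300 mg | 6–11: 100 mg; 12–16: 200 mg | – |
| 400 mg | 5–8: 100 mg; 9–12: 200 mg | 13–16: 300 mg or 200 mg |
| 600 mg | 3–5: 100 mg; 6–8: 200 mg; 12–16: 400 mg | 9–11: 300 mg or 200 mg |

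If 50 mg counts as a level, some lower counts also move to 50 mg (for example 100 mg for 9–16 doses).

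**Effect on a table (illustration).** Assume 3 participants each at 200 and 400 mg, and an event only in the moved participant. By daily dose taken: 1/3 (33.3%) at 400 mg and 0/3 at 200 mg. By Table 1: 0/2 at 400 mg and 1/4 (25.0%) at 200 mg.

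**Upward row.** A 200 mg participant who took 250 mg daily totals 21 × 250 = 5,250 mg. That is 5,250 / 6,300 = 83.3% of the 300 mg total, so where 300 mg counts as a level the label is 300 mg, again never taken.

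**DLT set.** The example participant missed 9/21 = 42.9% of doses for a non-DLT reason. The estimand leaves this participant out. If followed to Day 21, the third criterion makes the participant eligible as a 200 mg non-DLT. Protocol Table 17 says intercurrent events are dealt with through the DLT and DLT-set definitions, so the two texts ought to agree.

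**The case against.** The strongest defence is that cumulative exposure over the DLT window is a pre-specified convention, used alike in protocol Table 15, SAP 8.1 and Table 1. Leaving a participant with 12 of 21 doses at 400 mg also dilutes the 400 mg column with someone under-exposed. That cost is real and the fix must carry it. It does not rescue the label: an as-treated safety table headed 200 mg should not contain events that arose on 400 mg daily.

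Other points, and what stands of each:
- **Prorated denominator.** If planned dose were counted only up to Day 12, compliance would be 4,800 / 4,800 = 100% and nobody would move. The SAP's stated 21-day window favours the full-plan reading, but its wording does not wholly exclude the other.
- **Tie-break.** The 200 mg label relies on a rule borrowed from the DLT set. Any other choice in the example (100 or 50 mg) lies further from the dose taken.
- **Limited reach.** An adverse event preventing 80% delivery is itself a DLT criterion (protocol 6.6.2), and a confirmed DLT at no more than 100% of plan keeps the planned level. What remains is noncompliance, logistics, and adverse-event shortfalls not confirmed as DLTs.
- **PK.** SAP 8.1 analyses PK by the intervention actually received, and SAP 16.1.6 defines dose level in PK outputs as schedule and dose. Grouping by administered dose is therefore a permissible reading, although the SAP 8.1 note points back to Section 9. SAP 10.2.1 and 16.1.4 allow exclusion of PK values affected by missed doses; Day 1 and Day 8 profiles in the example precede any missed dose.
- **SMC discretion.** The SMC decides DLT evaluability and may weigh schedule deviations. The third criterion can also be read as covering only people dosed at another cohort's level. This settles individual cases but leaves two differing written defaults.
- **Visibility.** The both-ways exposure tables and participant listings would reveal a move, but would not correct the summary column.

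**Conclusion.** The concern holds for safety tables. As written, Table 1 can label a no-DLT participant with a daily dose never taken, for example 400 mg on 9–12 of 21 days shown as 200 mg, half the dose received. This assumes once-daily dosing, the full 21-day plan as denominator and the highest qualifying level. The documents give no expected frequency; with cohorts of about 3, a single case changes a column. The DLT-set and efficacy-grouping conflicts are textual and need reconciling whether or not such a case arises.

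Three stronger inferences are not supported:
- **That the MTD or dose-toxicity model will be biased.** Entry to the DLT set is subject to the SMC, and the size of any effect cannot be computed because the model prior is redacted.
- **That PK results by dose are wrong.** Table grouping is ambiguous. Dose normalisation uses the dose administered, and the power model refers to each participant's dose size.
- **That toxicity-driven stopping is hidden in lower-dose columns generally.** Confirmed DLTs at or below 100% of plan stay at the planned level.

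This should be corrected before database lock.

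**What to change.** 1. **Safety-table level (SAP Table 1).** Assign it by the pre-specified daily dose taken on most dosing days in the 21-day window, in both the downward and upward rows. Participants with only missed or stopped doses stay at the level they took. Use the 80% thresholds only for DLT evaluability. Requiring merely that the lower dose was taken at some point is not enough: 11 × 400 + 1 × 200 = 4,600 mg is 54.8% of plan, 73.0% of the 300 mg total and 109.5% of the 200 mg total, and would still move to 200 mg. State a default, such as planned level with a footnote, for anyone whose usual daily dose was not a pre-specified level.
2. **PK tables.** State that they are grouped by the dose administered on the PK day.
3. **DLT set.** Limit the third criterion to participants who took another cohort's daily dose for at least 80% of that cohort's planned dosing, so that it agrees with the estimand. Change SAP 8.1 now and protocol Table 15 at the next amendment.
4. **Lists and labels.** Name the levels that count as pre-specified, and choose one efficacy grouping for SAP 8.1 and Section 9.

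**Cost.** Mostly SAP wording; the Table 15 change needs IRB/IEC approval (protocol Appendix 2). Some under-exposed participants remain in the higher-dose column, so their compliance should be footnoted. Occasionally one fewer participant is DLT-evaluable; protocol 6.6.2 and 7.2 already allow replacement.

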At the discretion of the SMC, if the toxicity and tolerability profile of M4076 remains ambiguous at any DL, including the MTD or if additional PK/Pd data are felt necessary at any DL below the MTD, additional participants may be studied at that DL to better define the toxicity, tolerability, PK, and Pd. The study procedures for these additional participant(s)/cohort(s) will be the same as that specified for other study participants/cohorts.

This study part will also investigate the pharmacodynamics of M4076 as a secondary objective. Paired tumor biopsies (optional) and serial blood samples (mandatory) will be collected to evaluate markers of ATM inhibition.

If necessary, the Schedule of Activities will be adjusted, e.g. to ensure that PK and Pd samples are collected at the appropriate time points.

Once the MTD and/or RDE is determined in Part 1A, the RDE from Part 1A will be used for the food effect cohort in Part 1B.

Intraparticipant Dose Escalation: No intraparticipant dose escalation is allowed. However, upon declaration of safety and tolerability of the MTD or RDE by the SMC, participants who are still receiving ongoing study intervention at doses lower than the RDE may be switched to the RDE if participants have not experienced any treatment-emergent related AEs greater than Grade 1.

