6.6.2.1 Dose Interruptions and Modifications

Participants who experience an AE meeting DLT criteria during the DLT assessment period need to interrupt M4076 (Table 10). No dose modifications of M4076 should be made during the DLT assessment period for the dose escalation part of the study (Part 1A).

Participants who experience rash and systemic symptoms (e.g., fever, vomiting, diarrhea), or other signs of hypersensitivity should have M4076 discontinued immediately and are not to be rechallenged with any dose of M4076. Grade 2 and Grade 3 rash (without systemic symptoms) should be managed with treatment interruption and supportive medications, including topical or oral steroids.

Dose modifications outside the DLT period are allowed. Participants who experience a Grade 4 drug-related toxicity should discontinue treatment promptly. For a Grade 3 drug-related toxicity, M4076 treatment should be interrupted and may resume at a reduced dose provided the toxicity has resolved to Baseline value or Grade ≤ 1 within 2 weeks. At the first instance of a Grade 3 toxicity, study intervention will be held, and allowed to resume with a 25% dose reduction once said toxicity recovers to Grade ≤ 1 . Should a study participant develop a recurrent Grade 3 drug-related toxicity, study intervention will once again be held, and allowed to resume with a 50% dose reduction once said toxicity recovers to Grade ≤ 1 . Subsequent recurrences of Grade 3 toxicity will prompt discontinuation of study treatment, i.e., no more than 2 dose reductions will be permitted. Based on emerging data (i.e. toxicity, PK, Pd) and tablet strength availability, different dose reductions may be recommended as agreed between Sponsor and investigator, such as alternative dose reduction steps or different dosing regimen. Recommended dose reductions for each potential DL are provided in [Table 10](#).

Once the dose of M4076 has been reduced in an individual participant, it must not be escalated back to the original dose level. If more than 2 dose reductions of $> 50\%$ dose decrease are indicated, the participant will be permanently discontinued from study intervention. Consultation between Investigator and Sponsor about dose reduction is encouraged.

Table 10 M4076 Recommended Dose Modifications for Grade 3 Hematologic and Nonhematologic ADRs

Potential DLs – Starting doses	Grade 3 Hematologic and Nonhematologic ADRs		
	1 st occurrence DR of 25%	2 nd occurrence DR of 50%	3rd occurrence

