## 9.6 Definition of On-treatment Period

The on-treatment period is defined as the time from the first dose of study intervention day to the last administration day of study intervention + 30 days, or the cut-off date or death, whichever occurs first.

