## 15.2 Adverse Events

Adverse Events (AE) will be analyzed among the Safety analysis set and presented by dose level (and regimen if different regimens are tested) and overall, and by study part, if not otherwise specified.

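### Participants switched up to the RDE keep the dose label set in their first 21 days, so safety events that begin on the RDE are tabulated under a lower 'actual dose'

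*SAP*

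**What the plan says.** Protocol 4.1.1 rules out intraparticipant escalation in general but makes one exception. Once the SMC has declared the MTD or RDE safe and tolerable, "participants who are still receiving ongoing study intervention at doses lower than the RDE may be switched to the RDE". The exception is open only to those with no related treatment-emergent event above Grade 1. Protocol 6.6.2.1 adds, for Part 1A: "No dose modifications of M4076 should be made during the DLT assessment period".

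SAP Section 9 (Definition of actual dose) states that, unless otherwise specified, "analyses of safety, efficacy and PK parameters will be conducted by actual dose", and that "actual dose is determined by considering study drug compliance during the DLT evaluation period (first 21 days from first dose of M4076". DLT status is the other determinant. Compliance is the "cumulative actual dose taken by the subject divided by the cumulative cohort-level planned dose the subject was expected to receive", and SAP Table 1 converts it into one dose label per participant.

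SAP 15.2 has adverse events "presented by dose level (and regimen if different regimens are tested) and overall, and by study part". Treatment-emergent events are those in the on-treatment period, which SAP 9.6 defines as "the time from the first dose of study intervention day to the last administration day of study intervention + 30 days", cut short only by the cut-off date or death. A change of dose does not end or restart it. The worst on-treatment laboratory grades (SAP 15.4) and the notable ECG changes (SAP 15.6.2) use the same period.

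**The concern.** SAP 8.1 classifies participants in the safety set by the dose they actually received. A reader of a table by 'actual dose' will assume that the 100 mg column shows what happened on 100 mg. For a switched participant it also shows what happened afterwards on the RDE.

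Occurrence of adverse events is one of the endpoints under the primary dose-toxicity objective, and low-dose cohorts are planned at about 3 participants. The by-dose safety tables could therefore make a low dose look more toxic than it was and omit part of the experience on the dose chosen for expansion.

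**Working it through.** The plan gives no figure to reproduce, because the point concerns an attribution rule. The check applies that rule to a switched participant.

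**1. Order of events.** Dose changes are barred in the 21-day DLT period of Part 1A, so a permitted switch falls on Day 22 or later. The label is already set by then.

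**2. Label from SAP Table 1.** Take full compliance and no DLT. For a 100 mg cohort, compliance = (100 × 21) / (100 × 21) = 100%. The row for 80% to 100% without a DLT returns the planned dose level. The same holds for assumed switches of 100→200, 100→300, 200→300, 200→400, 300→400 and 100→600 mg, because nothing after Day 21 enters the formula. A higher label requires more than 100% of the planned dose within the 21 days.

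**3. Share of dosing under the lower label.** For a switch on day s and T days of dosing, the share is (T − s + 1) / T. The documents give neither s nor T. Protocol 4.1 gives about 105 days on study. The assumed values are T = 105; T = 105 − 28 (screening) = 77; and T = 105 − 28 − 30 (follow-up) = 47.

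| Switch day | T = 47 | T = 77 | T = 105 |
|---|---|---|---|
| 22 | 26/47 = 55% | 56/77 = 73% | 84/105 = 80% |
| 43 | 5/47 = 11% | 35/77 = 45% | 63/105 = 60% |

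Example: 100→300 mg on Day 22 with 105 days of dosing gives (100 × 21 + 300 × 84) / (100 × 105) = 27,300 / 10,500 = 260% of the planned dose over the whole treatment. The safety label is still 100 mg.

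**4. Which events are affected.** Only participants with no related treatment-emergent event above Grade 1 may switch. Unless an event is later regraded or its causality changed, every related event of Grade 2 or higher in a switched participant began after the switch. All of these count under the lower dose.

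**5. Effect on the columns.** The low-dose column keeps the participant and gains the event, so its rate can only rise or stay the same. One participant is 1/3 of a cohort of 3 (33 points) or 1/6 of a cohort of 6 (17 points). That is a property of cohort size and does not estimate the effect. The RDE column lacks both the participant and the event, so its rate could move either way.

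**6. Search for a correcting rule.**
- Attribution to the last treatment before onset (SAP 15.2) covers only the fed and fasted periods of Part 1B.
- The rules for more than 120% of planned dose (note to SAP Table 1; SAP 14) remove data from Pd or efficacy summaries, not from safety.
- Double presentation by planned and actual dose (SAP 9) applies to disposition, compliance and exposure, and only when the two labels differ. For a fully compliant switched participant they are the same.
- The fields listed for the adverse event listing (SAP 15.2.1) do not include dose at onset.

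No visible SAP text re-labels switched participants or separates their data at the switch.

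**The case against.** Reporting by a single dose level per participant is a coherent cohort convention, and participants whose dose is reduced also keep their 21-day label. On this view the SAP merely leaves switches unaddressed. The convention is defensible for a column described as the assigned cohort. The SAP, however, calls the label 'actual dose' and distinguishes it from planned dose, and following the stated rule puts RDE events under a lower dose. That goes beyond a missing detail.

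Several other objections stand and limit the point:
- Switching is optional and may never happen.
- The tables concerned are descriptive; the study tests no hypothesis.
- Events can be traced by hand. All administrations are listed, adverse event listings carry the treatment day, and the exposure table has a category for relative dose intensity above 120%.
- The TLF shells and the SMC analysis plan are not in the available text, so a rule there cannot be excluded.

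A reader might infer that the MTD or RDE decision is biased. The documents do not support that: a switch is possible only after the SMC's declaration, and the DLT and BLRM analysis rests on the 21-day DLT data. A reader might also infer that toxicity at the RDE is hidden and the dose-response flattened. That is not shown either. At least 6 participants must be treated at the MTD and/or RDE, so that dose has its own column. Switched participants are also selected for tolerance, so their events would not give an unbiased estimate of RDE toxicity.

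**Conclusion.** The point holds as a minor reporting defect that depends on switches occurring. If at least one participant is switched, safety findings that first occur on the RDE are tabulated under a lower 'actual dose'. The supported consequences are possible inflation of toxicity in small low-dose cohorts and the absence of those participants' RDE experience from the RDE column.

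The size cannot be stated, because the documents give neither the number nor the timing of switches. It is nil with no switches. For one switched participant, the share of dosing days under the lower label is 11% to 80% across the assumed scenarios. The conclusion assumes that the switch follows the 21-day window, as the protocol requires, and that no unseen document contains a rule for it. The primary DLT analysis is unaffected.

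**What to change.** Add a rule to SAP Section 9, referenced from the safety sections:

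- In by-dose safety summaries, include a switched participant's data only up to the switch date.
- Show their later events and assessments in a separate 'switched to RDE' table or column with its own denominator and exposure time. Do not pool them with participants who started at the RDE, because the eligibility condition selects those who tolerated the lower dose.
- Add dose at onset and a switch flag to the adverse event listings.
- Leave the DLT analysis unchanged.

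This changes reporting only. The cost is one derivation from dosing dates already collected and one extra display. There are two small downsides: switched participants appear in two columns, and delayed toxicity from the lower dose may fall in the post-switch display. A footnote should state both.
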